## 6.0 Procedures Involved

### Study Design

The study is an unblinded, 3-arm, randomized, controlled trial. After successful screening and consent, individuals will wear a blinded Dexcom G6 Pro CGM inserted 1 week after consent. Families who have previously used a CGM device

will be allowed to insert the G6 Pro during a remote visit. At the baseline visit (visit 1; day 1), participants will be randomized to the COIN2DOSE, LOAN2DOSE, or control treatment arms and will be trained on the procedures appropriate to their treatment arm. Participants will also complete baseline measures by questionnaire. Participants will complete procedures specific to their treatment arm weekly. Visit 2 will occur after 12 weeks (90 days). Participants will stop any treatment interventions after this visit. A1C and questionnaire measures will be completed, and participants will again wear the Dexcom G6 Pro CGM for 10 days (the device will be returned by mail post-visit). Participants will receive no treatment intervention from week 13 to week 24. Visit 3 will occur after week 24. Again, A1C and questionnaire measures will be completed and participants will wear the Dexcom G6 Pro CGM for 10 days. Participants who have their own CGM will wear it as usual and will not require a blinded Dexcom.

All study participants will also have the option to participate in a focus group discussion (FGD) regarding study participation.

Parents of children who meet inclusion criteria and participate in the study may also elect to participate in a focus group.

#### Study Visits

Study visits may occur in-person or remotely (i.e., from home). Procedures will be adapted to accommodate both scenarios.

## **7.0 Data and Specimen Banking**

#### Data Collection

Demographic data: Demographic data will be collected from the participant via an electronic data collection form in REDCap which shall serve as the source.

Demographic data will be verified with review of electronic medical record data. For remote visits, a web URL linking to the REDCap survey will be shared with participants.

A1C data: Participants will use a capillary A1C kit to collect a fingerstick A1C sample. An educational document and video (YouTube <https://youtu.be/e9loR3N4Rho>) have been created to educate approved study staff and participants on collection of the sample. The A1C is analyzed in a CMH lab by automated high performance liquid chromatography (reference range 4.0-6.0%, Tosoh 2.2, Tosoh Corporation, San Francisco, CA), which is a measurement method reliable to DCCT standards. The CMH A1C mail-in kit has excellent reliability to fresh samples ( $r=0.98$ ). Samples will be delivered to the Broadway lab by approved study staff for in-person study visits; samples will be mailed to the Broadway lab by participants completing remote visits from home. Sample tubes will be pre-labeled by study staff with the participant's study ID. If insufficient sample for analysis is collected at any time point, participants may be asked to repeat the sample collection to rescue data collection.

If participant does not return A1C mail-in-kit, point-of-care A1C or serum A1C may be used instead if available.

CGM data: Participants will use the Dexcom G6 Pro in blinded mode for data collection purposes only. If insufficient data for analysis are collected at any time point, participants may be asked to replace the CGM device to rescue data collection. No treatment decisions will be based on G6 Pro data. Dexcom G6 Pro data will be uploaded from the Dexcom receiver to Dexcom Clarity using the participant's personal, CMH-connected Dexcom Clarity account; data will then be collected as a .csv file for analysis. Files will be aggregated into a study database using MS Excel or equivalent software. Participants with their own CGM will use it as usual. They will be asked to share their CGM information with the study team per the usual procedure for diabetes clinic visits.

Insulin delivery data: Participants will use their personal, prescribed insulin delivery device throughout the study. Insulin delivery devices will be uploaded to Children's Mercy-approved software compatible with the specific device. Data will be uploaded to the participant's personal, CMH-connected account in the relevant upload system. Data will then be collected as a .csv file for analysis. Files will be aggregated into a study database using MS Excel or equivalent software. Insulin delivery systems and/or any date of system change will be noted at enrollment and on REDCap questionnaires.

Questionnaire data: All questionnaire data will be collected directly from participants via electronic (REDCap).

Focus group discussions: Focus group discussions (FGD) will optional and stratified by intervention arm. As the ideal size for FGDs are 6-8 participants, it is possible that we will conduct two FGDs per arm if there is enough interest among participants. Thus, we anticipate conducting 3-6 FGDs. FGDs will be approximately 90 minutes in duration, conducted by a trained moderator using a semi-structured guide. Both youth and their parents will be invited to participate in the focus groups.

FGDs will be conducted virtually on Microsoft Teams according to Standard Operating Procedures currently in pilot testing with the CMH Formative Research Team. De-identified data will be transcribed using Teams software and uploaded into Dedoose software for analysis.

Data and Specimen Banking

## **8.0 Genetic Analysis Information**

N/A

## **9.0 Sharing of Results with Subjects**

Results will not be shared with subjects.

## 10.0 Study Timelines

Table 1. Schedule of events

visit #	Visit 1	CGM placement	Intervention	Visit 2	Maintenance	Visit 3
		1 week post enrollment	1-12 week post CGM placement	3 months (+/-14 days)	12 weeks post visit 2	6 months (+/-14 days)
Consent	x					
Randomization	x					
CGM (10-day)		x*		x*		x*
A1C	x			x		x
Demographic	x			x		x
PHQ9	x			x		x
DTSQteen	x			x		x
MyQ	x			x		x
Wake Forest Physician Trust Scale	x			x		x
Perceived Involvement in Care Scale	x			x		x
Health-related empowerment scale.	x			x		x
Concerns about AI	x			x		x
Pump/pen** download	x		x	x	x	x
Focus Group Participation - Youth						x
Focus Group Participation - Parents						x

\*CGM will be returned by pre-paid, registered delivery service with tracking.

\*\* Control: pump/pen upload will occur monthly; COIN2DOSE and LOAN2DOSE pump/pen upload will occur twice weekly.

### Participant activities:

Participants enroll in COIN2DOSE	Participants randomized and fill out questionnaires Setting: at regularly scheduled standard of care (SOC) visit, in-person or virtual visit utilizing a CMH IRB approved remote platform.
1 week post enrollment	All groups will have Dexcom sensor inserted and will be worn x 10 days. Setting: in-person at the PCRU or virtual meeting.** Dexcom sensor may be mailed to participants. If mailed, the 1-week visit may take place via virtual visit utilizing a CMH IRB approved remote platform.  Participants with their own CGM will wear it as usual.
3 months post enrollment	Participants fill out questionnaires + have blinded Dexcom sensor inserted during SOC visit or virtual visit. Participants will wear Dexcom x 10 days. Setting: SOC visit, in-person or virtual visit utilizing a CMH IRB approved remote platform.
6 months post enrollment	Participants fill out questionnaires and wear Dexcom x 10 days. Dexcom inserted during SOC visit or virtual visit utilizing a CMH IRB approved remote platform. Setting: clinic or remote visit utilizing a CMH IRB approved remote platform.  Finally, participants return CGM by mail. (Not applicable to participants with their own CGM.)  Focus group discussions are conducted. Both youth and parents will be invited to participate.

\*\*Participants may choose to have in-person Dexcom insertion instruction at the PCRU or online via virtual instruction. If participant is Dexcom naive, they may insert Dexcom for the first time via online instruction, as it is a relatively simple procedure. If a participant is uncomfortable inserting the Dexcom for the first time virtually, they will have the option to do this with in-person instruction at the PCRU.

The link that patients will be sent for learning to use Dexcom is:

<https://www.dexcom.com/training-videos>

Participants with their own CGM will not be anticipated to require training; however, this will be offered if needed.

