### 2.2 Hypotheses

**Aim 1: To determine the impact of COIN2DOSE and LOAN2DOSE as compared to control on the trajectory of glycemic control and treatment engagement among adolescents age 12-17 years who are at risk for a near-term rise in A1C.**

Hypothesis 1: Use of COIN2DOSE will result in a lower rise in A1C compared to the controls.

Hypothesis 2: Use of COIN2DOSE will improve engagement as measured by mealtime insulin BOLUS score compared to controls.

Hypothesis 3: Use of COIN2DOSE will yield sustained improvements in A1C trajectory for 12 weeks after the intervention.

Hypothesis 4: Use of COIN2DOSE will yield sustained improvements in BOLUS score for 12 weeks after the intervention.

Hypothesis 5: Use of LOAN2DOSE will result in a lower rise in A1C compared to the controls.

Hypothesis 6: Use of LOAN2DOSE will improve engagement as measured by mealtime insulin BOLUS score compared to controls.

Hypothesis 7: Use of LOAN2DOSE will yield sustained improvements in A1C trajectory for 12 weeks after the intervention.

Hypothesis 8: Use of LOAN2DOSE will yield sustained improvements in BOLUS score for 12 weeks after the intervention.

**Aim 2: To determine the feasibility of COIN2DOSE and LOAN2DOSE interventions in adolescents age 12-17 years who are at risk for a significant near-term rise in A1C.**

Hypothesis 9: The COIN2DOSE intervention will be feasible as determined by 1)  $\geq 75\%$  of participants in the intervention group will complete all study procedures for the duration of the intervention and post-intervention study periods, 2)  $\geq 75\%$  of parents will endorse the feasibility of providing an equivalent economic incentive plan, and 3) no decrease in quality of life at visit 2 compared to baseline (visit 1).

Hypothesis 10: The LOAN2DOSE intervention will be feasible as determined by 1)  $\geq 75\%$  of participants in the intervention group will complete all study procedures for the duration of the intervention and post-intervention study periods, 2)  $\geq 75\%$  of parents will endorse the feasibility of providing an equivalent economic loss aversion plan, and 3) no decrease in quality of life at visit 2 compared to baseline (visit 1).

**Aim 3: To determine user satisfaction with the COIN2DOSE and LOAN2DOSE intervention in adolescents age 12-17 years who are at risk for a significant near-term rise in A1C.**

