## Secondary outcomes:

- 1) Change in A1C ( $\Delta A1C_{180\text{-day}}$ ) from baseline visit (visit 1) to 180-day visit (visit 3).
- 2) Change in percent time in range 70-180 mg/dL (%TIR70-180) from baseline visit (visit 1) to 90-day visit (visit 2) and to 180-day visit (visit 3).
- 3) Change in percent time hyperglycemic ( $>180$  mg/dL; %Hyper>180) from baseline visit (visit 1) to 90-day visit (visit 2) and to 180-day visit (visit 3).
- 4) Change in percent Time hypoglycemic ( $<70$  mg/dL; %Hypo<70) from baseline visit (visit 1) to 90-day visit (visit 2) and to 180-day visit (visit 3).
- 5) Change in percent Time severely hypoglycemic ( $<54$  mg/dL) (%Hypo<54) from baseline visit (visit 1) to 90-day visit (visit 2) and to 180-day visit (visit 3).
- 6) Change in mealtime insulin BOLUS score (BOLUS) from baseline visit (visit 1) to 90-day visit (visit 2) and to 180-day visit (visit 3).
- 7) For COIN2DOSE treatment group, proportion of participants who complete  $>90\%$  of study procedures throughout the intervention and post-intervention study procedures.
- 8) For COIN2DOSE treatment group, proportion of parents who endorse the feasibility of providing an economic incentive equivalent to that used in the intervention.
- 9) For COIN2DOSE treatment group,  $>75\%$  of participants will exhibit a score of  $>80\%$  total possible points on Diabetes Treatment Satisfaction Questionnaire (teen version)
- 10) Change in trust in provider from baseline visit (visit 1) to 90-day visit (visit 2) and to 180-day visit (visit 3).
- 11) For LOAN2DOSE treatment group, proportion of participants who complete  $>90\%$  of study procedures throughout the intervention and post-intervention study procedures.
- 12) For LOAN2DOSE treatment group, proportion of parents who endorse the feasibility of providing an economic incentive equivalent to that used in the intervention.
- 13) For LOAN2DOSE treatment group,  $>75\%$  of participants will exhibit a score of  $>80\%$  total possible points on Diabetes Treatment Satisfaction Questionnaire (teen version)
- 14) Change in perceived involvement in care from baseline visit (visit 1) to 90-day visit (visit 2) and to 180-day visit (visit 3).
- 15) Change in health-related empowerment from baseline visit (visit 1) to 90-day visit (visit 2) and to 180-day visit (visit 3).

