***Outcome Measures***

Hemoglobin A1C will be measured via a fingerstick capillary blood collection and analyzed on the Tosoh G8 HPLC. This approach is validated and traceable to DCCT standards.

CGM-derived glycemic metrics. Participants will have the Dexcom G6 Pro (blinded CGM) inserted 1 week after enrollment and at visit 1, and at visit 2. Participants will wear the CGM for 10 days following each insertion. We will consider >120 hours (>50% of total possible capture) of CGM data to be analyzable, otherwise data will be considered missing. Percent time in range (70-180), percent time >180, percent time >250, percent time <70, and percent time <54 mg/dL will be collected.

Participants who already have their own CGM will wear and use it as usual. They will not require a blinded Dexcom.

For patient-reported outcomes, questionnaires may be completed on iPad for in-person visit or via email or text via Twilio for remote visits. If completing by email or text, a link to REDCap will be sent to participant.

Quality of Life will be assessed using the MIND Youth Questionnaire (My-Q), which is a valid measure of quality of life for teenagers with diabetes (49).

Acceptability will be assessed based on treatment satisfaction scores using the Diabetes treatment Satisfaction Questionnaire, DTSQ-Teen, which has been validated for use in youth with T1D (50).

Trust in provider: Will be measured as a change score (visit 2-visit 1; visit 3-visit 1) with 10-items from the validated Wake Forest Physician Trust Scale (58).

Perceived Involvement in Care: Will be measured as a change score (visit 2-visit 1; visit 3-visit 1) with 13-items from the Perceived Involvement in Care Scale (59).

Health-related empowerment: Will be measured as a change score (visit 2-visit 1; visit 3-visit 1) with 8-items from the Health-related empowerment scale (60).

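### Nothing requires the visit 1 questionnaires to be completed before the unblinded allocation is disclosed, so the self-reported baselines are unprotected

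*Protocol*

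**What the plan says.** Section 6.0 (Study Design) states: "The study is an unblinded, 3-arm, randomized, controlled trial". For visit 1 it says that "participants will be randomized to the COIN2DOSE, LOAN2DOSE, or control treatment arms and will be trained on the procedures appropriate to their treatment arm", and the next sentence adds: "Participants will also complete baseline measures by questionnaire". In Section 10.0, the enrolment row under Participant activities reads "Participants randomized and fill out questionnaires". The visit 1 column of Table 1 in the same section lists consent, then randomisation, then (after A1C and demographics) the questionnaires.

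Visits may be in person or remote (Section 6.0, Study Visits). At remote visits the questionnaires may be completed through a link sent by email or text (Section 4.0, Outcome Measures).

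Four measures rest on the visit 1 questionnaire value as a baseline:

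- Trust in provider (Section 4.0): "Trust in provider: Will be measured as a change score (visit 2-visit 1; visit 3-visit 1".
- Perceived involvement in care (Section 4.0): "Change in perceived involvement in care from baseline visit (visit 1) to 90-day visit (visit 2", and likewise to visit 3.
- Health-related empowerment (Section 4.0): "Change in health-related empowerment from baseline visit (visit 1) to 90-day visit (visit 2", and likewise to visit 3.
- Quality of life on My-Q, one of the three feasibility criteria for each intervention (Section 2.2, Hypotheses 9 and 10): "no decrease in quality of life at visit 2 compared to baseline (visit 1".

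**The concern.** A baseline is meant to be free of the allocation. Here the arms differ in a way a teenager sees at once: earn up to $210, start with a virtual $210, or neither. If the forms are filled in after that news, pleasure or disappointment can colour answers about quality of life, trust, involvement or empowerment. The later score is then compared with a starting value that already carries part of the response to the arm.

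For the three change scores this would bias the contrast between arms. For My-Q the test is made within each intervention arm, so no control comparison can offset a shifted baseline. A lift at visit 1 could make a feasible intervention appear to fail, and a dip could hide a real fall. If sites or visit types use different orders, the problem would also vary between participants. The pilot is meant to inform a definitive trial (Section 3.2), so an unprotected order could be carried forward.

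**Working it through.** The plan gives no figure on this point, so there is none to reproduce. The check is of the text, followed by short algebra.

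**Order of events at visit 1**

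| Place | Order named | Connecting word |
|---|---|---|
| Section 6.0, Study Design | randomisation, arm training, questionnaires | also |
| Section 10.0, Table 1, visit 1 column | consent, randomisation, questionnaires | none (rows) |
| Section 10.0, Participant activities, enrolment row | randomisation, questionnaires | and |

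All three places name randomisation first. None says that the questionnaires must precede disclosure, and none says outright that they follow it. Staff who disclose the arm first comply with the text, and so do staff who collect the forms first.

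**What could act on the answers at visit 1.** Section 5.0 starts the payments and deductions one week after randomisation. Only knowledge of the arm and the arm training could influence visit 1 answers.

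**How a shift passes through.** Let m0 and m1 be an arm's mean scores at visit 1 and at follow-up without any disclosure effect, and let b be the shift in its visit 1 mean caused by knowing the arm.

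- Observed mean change = m1 - (m0 + b) = (m1 - m0) - b.
- Error in the difference in change, intervention minus control = -(b_intervention - b_control). An equal shift in both arms cancels.
- Error in the within-arm My-Q change = -b. Nothing cancels.

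**Illustrative size, three change scores only.** Inputs: 12 per arm (target of 36 in Section 13.0, allocated 1:1:1) or 24 per arm (maximum of 72). Assumptions not taken from the documents: the arms' baseline shifts differ by 0.1 to 0.3 SD; the SD of change equals the SD of the score, which requires a correlation of 0.5 between visits; no missing data.

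- Standard error of the difference in mean change = SD × sqrt(2/n).
- n = 12: sqrt(2/12) = 0.408 SD. Ratios: 0.1/0.408 = 0.25 and 0.3/0.408 = 0.74.
- n = 24: sqrt(2/24) = 0.289 SD. Ratios: 0.1/0.289 = 0.35 and 0.3/0.289 = 1.04.

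The bias does not shrink as the sample grows. It becomes larger relative to the standard error.

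**The case against.** The strongest reply is that the sequence is inferred. The linking words list what happens at a visit and set no order, and these sections are not always chronological. In Section 6.0, stopping the intervention after visit 2 is mentioned before the visit 2 measurements. In Table 1, the CGM row, first due a week after enrolment, sits above A1C and the questionnaires. In the 6-month activities row, wearing the sensor is mentioned before inserting it. This stands. A reader might infer that the protocol orders the forms to be completed after randomisation, and the text does not support that. What remains is that every listing points one way and nothing protects the baseline.

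Four wider readings also go beyond the documents:

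- **All questionnaire endpoints.** The DTSQ-Teen endpoints in Section 4.0 are score thresholds, so no visit 1 value is subtracted.
- **The primary outcome.** A1C is a laboratory measurement, and learning the arm cannot move it within the visit. Section 20.2 lists quality of life among its model's predictors but does not say which visit's value enters, so no effect on that model can be shown.
- **Depression as a compromised covariate.** Section 4.0 names PHQ-A as a covariate, but the model in Section 20.2 does not include it.
- **The size of the bias.** The 0.1 to 0.3 SD shift has no source in the documents, and the between-arm standard error does not apply to the within-arm My-Q rule.

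It is also fair to say that money is a less obvious influence on trust in a physician than on mood. The documents give no way to settle that.

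**Conclusion.** The point holds in a limited form. The protocol leaves the self-reported baselines open to influence by the allocation. Three secondary change scores (trust, perceived involvement, empowerment) and the My-Q feasibility rule are exposed. A1C and the DTSQ-Teen thresholds are not.

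The direction follows from the algebra: on a scale where higher is better, a lift at visit 1 understates later improvement in that arm, and a dip overstates it. The size is unknown; the standard-error ratios are illustrative and rest on the stated assumptions. The conclusion assumes only that the youth can learn the arm before submitting the forms, which the text permits. This is worth correcting because the remedy is specific and nearly free, but it does not threaten the primary comparison.

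**What to change.** State in Section 6.0 and in Section 10.0 (Table 1 and Participant activities) that every visit 1 questionnaire is completed and submitted before the participant's allocation is disclosed and before arm training starts. Reorder the visit 1 descriptions to match. For remote visits, say explicitly that the emailed or texted forms must be received first. Recording the time of disclosure would let the order be checked against form submission.

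The baseline A1C sample need not be tied to this rule. Doing so would gain nothing and could delay remote participants who post their kits.

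The cost is small. In person, the steps of one visit are reordered. Remotely, disclosure may have to wait until the forms are in, which may need a further contact. Sample size, endpoints and analysis are unchanged.

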## **5.0 Study Intervention**

To identify an at-risk population for more intensive intervention opportunities, the Children's Mercy Diabetes Center now routinely uses a validated prediction model based on advanced machine learning (random forest method) and natural language processing to identify individuals who are predicted to experience a rise in A1C in the next 90 days. The model analyzes all patients who presented for a diabetes visit in the prior week. To accomplish this task, the complete health record for the CMH Diabetes Center registry is analyzed. We will select patients from this cohort for recruitment into the present study.

**COIN2DOSE intervention:** From one-week post-randomization to the 12-week study visit, youth randomized to this treatment arm will receive personalized feedback via monetary incentives for dosing insulin at mealtimes. We will define mealtimes based on hour of the day and the presence of a carbohydrate entry associated with the insulin bolus. According to the methodology for calculating BOLUS(1) breakfast will be 0600-1000, lunch will be 1100-1500, and dinner will be 1600-2200. Thus, we will reimburse youth up to \$0.50 per mealtime with at least one meal-associated (carbohydrate-associated) insulin bolus completed (maximum \$1.50/day). We will offer the opportunity for youth to earn a bonus reimbursement of up to \$5.00/week for weeks during which they achieve at least 5 days of 3 mealtime insulin boluses. Finally, we will pay youth up to \$2.00 per week for sharing their insulin use data at least two times per week with the study team during the three-month treatment phase (maximum \$24.00). Therefore, maximum total incentive available is \$210.

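### Blinded-sensor CGM: the baseline wear can fall wholly within the incentive period, and the visit-2 wear falls after it ends, so secondary outcomes 2 to 5 do not measure the change they define

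*Protocol*

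**What the plan says.** **What is to be measured.** Protocol section 4.0 defines secondary outcomes 2 to 5 as changes in CGM percentages (70-180, above 180, below 70 and below 54 mg/dL) from visit 1 to visit 2 and to visit 3. On wear it says: "Participants will wear the CGM for 10 days following each insertion".

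**When the intervention runs.** Section 5.0, for COIN2DOSE: "From one-week post-randomization to the 12-week study visit, youth randomized to this treatment arm will receive personalized feedback". The LOAN2DOSE paragraph sets the same window for deductions. Section 6.0 says of visit 2: "Participants will stop any treatment interventions after this visit". It adds: "Participants will receive no treatment intervention from week 13 to week 24".

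**When the baseline sensor goes in.**
- Section 10.0 (Table 1 and the participant activities) puts randomisation at visit 1/enrolment and the sensor one week later: "All groups will have Dexcom sensor inserted and will be worn x 10 days".
- Section 6.0 tells it in another order. After consent, "individuals will wear a blinded Dexcom G6 Pro CGM inserted 1 week after consent"; then "At the baseline visit (visit 1; day 1), participants will be randomized to the COIN2DOSE, LOAN2DOSE, or control treatment arms". The gap between insertion and visit 1 is not stated.
- Section 4.0 lists insertions one week after enrolment, at visit 1 and at visit 2, and none at visit 3, although sections 6.0 and 10.0 require one there.

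**When the visit-2 sensor goes in.** At 3 months, section 10.0 says participants "have blinded Dexcom sensor inserted during SOC visit or virtual visit". Section 6.0 agrees, and has the device mailed back after the visit.

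Participants with their own CGM keep using it and need no blinded sensor.

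**The concern.** A change score for an intervention trial should run from a reading before the intervention to one during it or at its end. Here the blinded-sensor schedule can do the opposite: the baseline reading on intervention, the 90-day reading off it.

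The two halves differ in kind. The baseline problem is a contradiction, because staff following different sections would collect different baselines. The visit-2 problem is a consistently stated design choice that does not serve the outcome it feeds.

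If dosing behaviour responds quickly to incentives, an on-intervention baseline removes part of the effect from the change, in the active arms only. If the effect fades once incentives stop, an off-intervention follow-up removes more. Any rise in time below 70 or 54 mg/dL could be missed in the same way. Section 3.2 itself reports an incentive trial of glucose monitoring whose effect did not last through the 90 days after payment stopped, and treats persistence as unresolved. It does not show how fast an effect fades.

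No analysis can recover sensor days that were never recorded, so a statistical analysis plan could not fully repair this.

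**Working it through.** **Length of the intervention.** The plan's $210 maximum reproduces: a full week pays 7 × $1.50 + $5.00 + $2.00 = $17.50, and 12 × $17.50 = $210. The maximum therefore assumes 12 paid weeks. From day 7 these end on day 7 + 84 = day 91.

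**Baseline overlap** (days of a 10-day wear that are on intervention; day 0 = randomisation unless stated):

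| Source of sensor timing | Wear | Intervention starts | Overlap |
|---|---|---|---|
| Section 10.0 sensor, section 5.0 start | days 7-17 | day 7 | 10 of 10 |
| Section 10.0 sensor, Table 1 start read as one week after placement | days 7-17 | day 14 | 17 − 14 = 3 of 10 |
| Section 4.0 insertion at visit 1, section 5.0 start | days 0-10 | day 7 | 10 − 7 = 3 of 10 |
| Section 6.0 order, visit 1 falling s days after insertion (day 0 = insertion) | days 0-10 | day s + 7 | max(0, 3 − s) |

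For section 6.0, s = 0, 1, 2 and 3 or more give 3, 2, 1 and 0 days. The document does not give s.

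Table 1 counts the intervention as weeks 1 to 12 from sensor placement. Read as the first through the twelfth week, it starts on day 7, agrees with section 5.0, and the overlap is 10 of 10. The second row applies only if the intervention starts one week after placement.

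**Visit-2 overlap.** With visit 2 on day v, wear runs from v to v + 10.
- Under sections 5.0 and 6.0 the intervention ends at v. Overlap is 0 of 10 for any v, including the window limits 90 − 14 = 76 and 90 + 14 = 104.
- If 12 paid weeks ran to day 91 despite the stop in section 6.0, overlap is max(0, min(10, 91 − v)): 10 days at v = 76, 7 at v = 84, 1 at v = 90, and 0 at v = 91 or 104.

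The second case exposes a further mismatch. Ending at a day-84 visit leaves (84 − 7)/7 = 11 paid weeks, or $192.50. Ending at day 90 leaves 83/7 = 11.86 weeks, or about $207.50. Neither reaches $210.

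**Moved wear.** If the visit-2 sensor is worn from v − 10 to v and the intervention ends at v, overlap is 10 of 10 for every v above.

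**Shortened baseline.** Insertion at visit 1, counting only days before a day-7 start, gives at most 7 × 24 = 168 h. Section 4.0 requires more than 120 h: 120/168 = 71% capture, against 120/240 = 50% for a full wear.

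**The case against.** The strongest reply is that section 6.0, the study-design section, describes the sensor before the randomisation visit and so intends a pre-randomisation baseline. That has weight. In that order visit 1 cannot precede insertion, so overlap is at most 3 days, and it is nil once visit 1 is 3 or more days after insertion. A reader might infer larger overlaps by putting visit 1 at consent, but that breaks section 6.0's own sequence. Even so, section 10.0 places consent and randomisation at one visit with the sensor a week later, and it is the schedule staff would work from.

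Second, section 4.0 lists three insertions, as section 10.0 does. Its odd list may be a visit-numbering slip rather than a rival schedule. That is plausible; it still needs correcting.

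Third, the 12-week maximum and Table 1 could be taken to carry the intervention past visit 2. The explicit stop in section 6.0 makes 0 of 10 the better reading, but these passages do pull against each other.

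Fourth, a reader might extend the point to participants with their own CGM because no data window is fixed for them. The document does not support that: which of their days count is a data-handling rule commonly left to the statistical analysis plan, and no overlap is shown for them.

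Fifth, only secondary outcomes of a pilot are affected. That stands, and it limits the severity.

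**Conclusion.** The point holds for blinded-sensor users and secondary outcomes 2 to 5, and should be fixed. Following sections 5.0 and 10.0 as written gives 10 of 10 baseline days on intervention in the active arms; other readings give 3, or 0 to 3. The visit-2 wear has 0 of 10 days on intervention unless 12 paid weeks override the stop in section 6.0.

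The 90-day CGM change can therefore be attenuated, cancelled or reversed, and baseline overlap carries into the 180-day change. These are possibilities. They depend on how quickly the effect appears and fades, which the document does not give, and the share of participants on the blinded sensor is not given either. No effect size is estimated.

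A reader might infer that the trial's main result is compromised. It is not: the primary outcome is A1C at the visits, and none of the 12 hypotheses in section 2.2 rests on CGM. The loss is to the CGM estimates, which matters because section 3.2 wants the pilot to inform power calculations for a definitive trial.

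**What to change.** Change the measurement schedule and leave the intervention as it is.

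1. **Baseline.** Reconcile sections 4.0, 5.0, 6.0 and 10.0 to one CGM schedule in which baseline data precede the start of incentives.
   - *Cheapest:* insert at visit 1 and count only days before incentives start. Cost: at most 168 h of data, so 71% capture is needed instead of 50% and more baselines may be missing; the baseline is shorter than the 10-day follow-up and is worn after unblinded allocation.
   - *Alternative:* insert before randomisation, as section 6.0's order implies. Three days between insertion and visit 1 are enough to keep the wear ahead of a day-7 start; a 10- or 17-day gap from consent to randomisation is not a requirement. Cost: consent is separated from visit 1, which Table 1 combines.
2. **Visit 2.** Insert the sensor about 10 days before the booked visit, by the mailing and remote insertion section 10.0 already allows. Cost: one extra remote contact and no additional sensors. If the wear stays where it is, label the visit-2 CGM outcomes as post-incentive.
3. **Text.** List the visit-3 insertion in section 4.0. Reconcile Table 1's intervention window, the 12 weeks implied by $210, and the stop at visit 2.
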